10.2 Safety Review

Both the risks listed in Section 4.1 and unknown risks will be monitored as follows: Patients will be visited daily to determine if the device placed is working. Medical records will be reviewed for off hours and weekends. Any failure or complication from the midline catheter or ultrasound guided IV will be documented within redcap. Any complication or failures will be emailed to the study investigator to review the chart and or contact the patient to severity, seriousness, relatedness, and expectedness. It is expected that both midline as well as ultrasound guided IVs will be associated with routine bleeding, pain, swelling and failure. Any complication that requires intervention by a surgical or procedural intervention will be reported. Placement of a new vascular access device will not be considered a complication. As ultrasound guided IVs as well as midline catheters are approved for use at Boston Medical Center and are considered generally safe procedures we do not expect trends that could affect subject safety.

10.3 Reporting Plans

The Principal Investigator at BMC/BU Medical Campus will report Unanticipated Problems, safety monitors’ reports, and Adverse Events to the BMC/BU Medical Center IRB in accordance with IRB policies:

- Unanticipated Problems occurring at BMC/BU Medical Campus involving a fatal or life-threatening event will be reported to the IRB within 2 days of the investigator learning of the event.
- Unanticipated Problems occurring at BMC/BU Medical Campus not involving a fatal or life-threatening event will be reported to the IRB within 7 days of the investigator learning of the event.
- Reports from safety monitors with recommended changes will be reported to the IRB within 7 days of the investigator receiving the report.
- Adverse Events (including Serious Adverse Events) will be reported in summary at the time of continuing review, along with a statement that the pattern of adverse events, in total, does not suggest that the research places subjects or others at a greater risk of harm than was previously known.

- Reports from safety monitors with no recommended changes will be reported to the IRB at the time of continuing review.

10.4 Stopping Rules

The study has no stopping rules.

There are no expected reasons a subject will be removed from the study.

It is not expected that the study will be stopped as both devices being used are currently a part of standard clinical care.

11 Data Handling and Record Keeping

11.1 Confidentiality

We will store information in ways that are secure. We will store paper files in locked filing cabinets. We will store electronic files in computer systems with password protection and encryption. All patient information will be de-identified as soon as possible with a study ID number. We do not anticipate needing to share data. We will update clinicaltrials.gov with study findings but not share individual patient data.

Patients will be enrolled using paper consent forms. Forms will be placed into locked filing cabinet in the office of the department of emergency medicine. Patients will be assigned a study ID at the time of enrollment to immediately de-identify all patient information as possible. Patient name, date of birth and MRN will be stored on the hospital G drive in a password protected file that only study staff have access to. The study monitor or other authorized representatives of the sponsor may inspect all documents and records required to be maintained by the investigator, including but not limited to, medical records (office, clinic, or hospital) and pharmacy records for the subjects in this study. The clinical study site will permit access to such records.

11.2 Source Documents

Source data will include any clinical information in the medical record. Source data will also include images stored from the ultrasound guided procedures (UGPIV or MC). Source data will also include patient surveys. All source data will be stored in locked file cabinets or within electronic files stored on the hospital G drive as already done with other approved IRB study protocols.

Data generated by the methods described in the protocol will be recorded in the subjects' medical records and/or study progress notes. Data may be transcribed legibly on CRFs supplied for each subject or directly inputted into an electronic system or any combination thereof.

11.3 Case Report Forms

The study case report form (CRF) will be the primary data collection instrument for the study and will only exist in electronic entry. All data requested on the CRF will be recorded. All missing data will be explained. If a space on the CRF is left blank because the procedure was not done or the question was

not asked, "N/D" will be recorded. If the item is not applicable to the individual case, "N/A" will be recorded. All entries will be entered electronically directly into REDcap. Only paper forms will be the patient consent form and physician scanning report form, and patient survey. All of these are supplemental forms.

11.4 Study Records Retention

Boston Medical Center requires that study records be retained for at least seven years after completion of the study. The BMC/BU Medical Campus IRB requires that documentation of informed consent of subjects be retained for at least three years after the study is closed, unless the IRB waived the requirement for informed consent or documentation of informed consent. These records will be saved in locked file cabinets or as retained in password protected files on department servers.

12 Statistical Plan

12.1 Study Hypotheses

The primary hypothesis is that midline catheters will be superior to ultrasound guided IVs with relation to survival time.

Secondary assessment will 1) attempt to prove that MC are superior to UGPIV with relation to cost effectiveness despite their overall higher upfront cost. 2) Patients will experience similar pain between MC and UGPIV, however will prefer the MC knowing the survival of the catheter is longer.

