Population:	Patients seen in the emergency department who meet criteria for DVA and study eligibility will be approached for enrollment by research staff. Inclusion criteria include: Expected inpatient admission for 72 hours or more, Age 18 or older, able to provide consent, English speaking, expected inpatient admission, two staff have looked for IV access or patient has history of requiring ultrasound guided IV. Exclusions: Prisoner, not suspected of having bacteremia, No phone number for follow up, Pregnancy, known to require long term IVA with a CVC or MC, no target vessel <1.6cm in depth, or do not have an upper extremity (left or right arm) that can accept a deep venous IV (example dialysis fistula in one arm and upper extremity deep venous thrombosis in the contralateral arm). Minimum sample size of 108, 54 in each study arm to be appropriately powered for this clinical question. It is likely we will need to enroll more than 108 after exclusions and randomization to ensure we obtain 54 in each arm.
Intervention:	Patients will be randomized to receive a standard UGPIV that is 4.88cm in length or a 10cm midline catheter.
Objectives:	
Aim 1: To determine if UGPIVs have a higher failure rate than midline catheters within 72 hours of placement.
 
Aim 2: To perform a direct cost analysis of UGPIV against that of the midline catheter over the length of the hospitalization.
 
Aim 3: To determine experience and satisfaction with each device to determine patient preference.

Design/Methodology:	A convenience sample of patients will be randomized to one of two arms. The first arm will receive standard UGPIV. The second arm will receive a MC. Patients will be randomized based on pre-randomized patient enrollment packets. Patients will receive one of two venous access options either the UGPIV or the MC in the ED. Catheter survival will be assessed based on time to when a failed catheter is found to be dysfunctional or when a catheter is removed

	by hospital staff. Study personnel will review medical records and visit patients daily Monday to Friday to assess how the IV is working. They will check to make sure that catheters have not been removed and have not malfunctioned by speaking with the patient or hospital staff.
Total Study Duration:	Expected April 1, 2018 to June 30 th , 2019

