4.1 Study Objectives

Aim 1: To determine if UGPIVs have a higher failure rate than midline catheters within 72 hours of placement.

There are several reasons why UGPIVs may fail. UGPIVs are shorter than midline catheters, and shorter catheters may fail due to infiltration which can be a result of malposition as well as having the catheter pull out of the vessel. We suspect that by using a midline catheter with a guidewire for placement with additional catheter length placed into the vessel, midlines will be superior to UGPIVs with regards to survival time of the catheter.

Hypothesis: Midline catheters have a lower failure rate at 72-hours compared to ultrasound guided peripheral IVs.

Aim 2: To perform a direct cost analysis of UGPIV against that of the midline catheter.

This study will not be large enough to complete a robust cost effectiveness analysis to compare UGPIV to midline catheters. As a part of this study we will collect information including but not limited to: the number of catheters used for IVA attempts, time for placement of each device, complications, and need for additional IV access during hospitalization (MC, PIV, or CVC).

Hypothesis: Midline catheters are a cost effective change in clinical practice due to lower complication rate and longer dwell times.

Aim 3: To determine patient experience and satisfaction with each device to determine patient preference.

Our goal will be to compare UGPIV to MC for patient experience (including pain, satisfaction, and preference) based on survey.

Hypothesis: Pain scores will be similar between the UGPIV and MC group, however patients will prefer the placement of the MC.

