4.1.2 Secondary Outcome Measures

Secondary outcomes will be determined based on review of the clinical record and patient responses to a questionnaire. All procedures that are performed including placing an IV and removing an IV should be available to determine additional costs associated with IV access during the hospitalization.

Responses for each of the questions on the study questionnaire will be compared between the study groups. Appropriate statistical tests will be used for bivariate, categorical, or continuous variables.

5 Study Design

This is a convenience sample, randomized controlled trial to determine if the midline catheter is superior to the ultrasound guided IV with respect to survival at 72 hours. Folders will be sealed and pre-randomized using computer number randomization. Patients will be screened for enrollment in the emergency department. Patients will be considered eligible for enrollment if they are considered a difficult vascular access patient and are expected to require hospitalization after physician assessment. We have selected patients who are felt to require admission as the midline catheter is indented for longer dwell times and are attempted to screen for patients who are likely to require IV access for a minimum of two hospital nights. There will be two arms 1) those randomized to standard care with ultrasound guided IV, and 2) those randomized to receive a midline catheter. Data will be collected from the medical record into redcap as well as an enrollment log stored on the hospital G drive. These will be password protected. Data will also be stored on QPATH which is a secure software for storing medical imaging (ultrasound images). Data lastly recorded on paper sheets including consent forms will be stored in locked filing cabinets with only study personnel access. Data will be collected directly from the patient as well as from the medical record.

6 Potential Risks and Benefits

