12.2 Sample Size Determination

Previous work suggests a failure rate of UGPIV of 40-44% and 5% for a small study of midlines placed in an ICU. We have therefore estimated a sample size based on a 25% difference in survival between midline catheter and UGPIV. **Based on a 25% difference in expected survival we will require 54 patients with a power of 0.8 and alpha of 0.05 assigned to each study arm (UGPIV and Midline).** Based on an expected 25% refusal rate and 30% of patients not being able to provide consent we will need to review and approach approximately 168 DVA patients. At BMC we place approximately 1600 ultrasound guided IVs per year making enrolling 54 in each arm highly feasible.

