We additionally will capture the time spent placing each UGPIV in comparison to midline catheters. This will be accomplished by using the timestamp on the ultrasound at time of vessel identification, and then again at time of successful documentation of the catheter within the vessel. We will estimate for each failure of IV access a four-hour delay to have it replaced once hospitalized. Based on geographic cost, it is about \$100 per hour for inpatient hospitalization in Massachusetts. We additionally estimate the cost for staffing to be \$100 to replace a midline or UGPIV. We anticipate approximately a 5% failure in the midline group and 40% failure in the UGPIV group. We anticipate all midline failures will require repeat midline or CVC placement. We anticipate 10% of UGPIV will go on to get a CVC due to medical needs. We additionally estimate 33% of patients in the UGPIV group will require replacement during hospitalization. We anticipate one patient in the UGPIV to get a CVC and have a complication. CVC complications are reported to cost \$15,000 to \$50,000, however we will estimate a \$30,000 cost for each complication (example pneumothorax or line infection).¹²

Cost Estimate for 54 patients in UGPIV group:

54 initial UGPIV placements (54 x \$371): Projected outcomes: 5 patients progress to needing CVC (5 x \$1338), 17 subsequent failures getting repeat UGPIV (17 x \$371), 22 total failures at \$500 in estimated cost from delays in care and staffing (22 x \$500), 18 patients require additional access past 72-hour dwell time limit and get repeat UGPIV (18 x \$371). One CVC complication in the group of 54 patients: (1 x 30,000). = **Total Estimate: \$80,709**

Cost Estimate for 54 patients in Midline group:

54 initial midline placements (54 x \$1338), 3 failures with replacement cost and staffing and hospital delays (3 x \$1338 & 3 x 500), No complications expected or need for CVC. **Total Estimate: \$77,766**

We have projected a slight decrease in cost for midline placement at \$77,766 vs \$80,807 for 54 patients in this study. Based on these values with a power of 0.8 and alpha of 0.05 using a two

tailed t-test for independent means to predict a sample size with a SD of \$3,000 we will need to enroll 34 patients to adequately power our cost comparison group.

Aim 3: We will compare patient survey responses based on descriptive statistics, chi-square tests, or t tests as appropriate.

13 Ethics/Protection of Human Subjects

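### The plan hypothesises similar pain in the two arms but gives no criterion that could support similarity; a non-significant difference test would not show it

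*Combined protocol and SAP*

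**What the plan says.** The pain hypothesis appears twice. Section 4.1 (Aim 3) states "Pain scores will be similar between the UGPIV and MC group", and section 12.1, within the Statistical Plan, states "Patients will experience similar pain between MC and UGPIV". In both places it is paired with an expectation that patients will prefer the midline.

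Pain is collected as part of "patient experience (including pain, satisfaction, and preference) based on survey". For analysis, section 12.3 (Aim 3) says "We will compare patient survey responses based on descriptive statistics, chi-square tests, or t tests as appropriate". Section 4.1.2 says that questionnaire responses will be compared between the groups and adds "Appropriate statistical tests will be used for bivariate, categorical, or continuous variables".

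The documents give no pain scale, no SD, no margin defining similar, no interval criterion, and no rule for deciding whether the pain hypothesis was supported. The sample size in section 12.2 rests on the failure comparison only: "Based on a 25% difference in expected survival we will require 54 patients with a power of 0.8 and alpha of 0.05".

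**The concern.** A t test or chi-square test takes no difference as its null hypothesis. A significant result speaks against similarity. A non-significant result is what one would see if pain were truly alike, but also if the data were too imprecise to show a difference, and the p-value does not separate the two. If a non-significant result were taken as support, noisier pain scores or fewer completed surveys would make the hypothesis easier to confirm.

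Section 6.3 says the comparison of failure, cost and patient preference is meant to help guide future IV access. A statement that pain is similar would be part of that message, so it should rest on an analysis able to support it.

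**Working it through.** **Inputs from the documents.** 54 per arm, 1:1, power 0.8, alpha 0.05 (section 12.2 and the synopsis: "Minimum sample size of 108, 54 in each study arm"). UGPIV failure 40-44% (section 12.2: "Previous work suggests a failure rate of UGPIV of 40-44% and 5% for a small study of midlines placed in an ICU"), with a planned difference of 25 points.

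**Inputs assumed.** Two-sided alpha for the sample size and for the pain comparison. Pain results are given in SD units because no scale or SD is stated. A 0-10 scale with SD 2 to 3 and a 1-point difference are used for illustration only.

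**1. The plan's own figure.** Take 44% against 19%, the upper end of the quoted UGPIV range less 25 points, with the pooled-variance formula and no continuity correction:

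n = [1.960·√(2·0.315·0.685) + 0.842·√(0.44·0.56 + 0.19·0.81)]² / 0.25² = (1.2875 + 0.5325)² / 0.0625 = 53.0005, which rounds up to 54.

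So 54 per arm reproduces. It is a calculation for catheter failure; pain does not enter it.

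**2. Precision for pain at 54 per arm.** The standard error of the mean difference is SD·√(2/54) = 0.192 SD. The 95% CI half-width is t(0.975, 106) × 0.192 SD = 1.983 × 0.192 SD = 0.38 SD.

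**3. Chance that a real difference is non-significant** (two-sided t test, noncentral t, 106 df):

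| True difference | Power | Non-significant |
|---|---|---|
| 0.2 SD | 18% | 82% |
| 0.3 SD | 34% | 66% |
| 0.4 SD | 54% | 46% |
| 0.5 SD | 73% | 27% |
| 0.6 SD | 87% | 13% |

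The balance point is about 0.38 SD: below it, non-significance is the more likely outcome; above it, the less likely. The difference detectable with 80% power is (1.960 + 0.842) × 0.192 SD = 0.54 SD.

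**4. In points on an assumed 0-10 scale:**

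| SD | 95% CI half-width | Power, 1 point | Power, 1.5 points | Power, 2 points |
|---|---|---|---|---|
| 2 | 0.76 | 73% | 97% | >99% |
| 2.5 | 0.95 | 54% | 87% | 98% |
| 3 | 1.14 | 40% | 73% | 93% |

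A true 1-point difference would therefore be missed 27%, 46% or 60% of the time. A 2-point difference would rarely be missed.

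**5. What 54 per arm could support if similarity were tested directly.** For two one-sided tests at 0.05, 80% power and a true difference of zero, n per arm = 2·[(1.645 + 1.282)/margin in SD]²:

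| Margin | n per arm for 80% power | Power at 54 per arm (simulation) |
|---|---|---|
| 0.3 SD | 191 | 1% |
| 0.4 SD | 108 | 33% |
| 0.5 SD | 69 | 65% |
| 0.6 SD | 48 | 86% |

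The planned sample reaches 80% power at a margin of about 0.57 SD, or about 0.63 SD if the 95% CI rather than the 90% CI must lie inside the margin.

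**The case against.** The strongest reply is that the plan never says how similarity will be judged. A reader might infer that the investigators intend to treat p>0.05 as proof of similar pain. The documents do not support that: no section states such a rule. What they show is a hypothesis without a criterion.

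Nor is the planned analysis only a difference test. Section 12.3 lists descriptive statistics first and assigns no particular test to pain, so reporting pain by arm descriptively is already allowed. That brings the plan close to estimation; what is missing is the interval and a statement that the conclusion rests on it.

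A reader might also infer that a non-significant result is likely whenever pain differs. That holds only for differences below about 0.38 SD. For a 1-point difference it requires an SD above about 2.6 (1/0.38), and differences of 1.5 to 2 points would be detected with power of 73% or more across the assumed SDs.

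Finally, the pain statement can be read as an expectation rather than a confirmatory claim. In section 12.1 the language of proof is attached to cost, and Aim 3 is mainly about preference. This is a fair reason not to insist on a formal equivalence test. It does not remove the gap: the statement stands as a study hypothesis in two sections, and none of the named analyses comes with a criterion by which it could be supported.

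**Conclusion.** The point holds as a mismatch between hypothesis and analysis. Similar pain is hypothesised, the named tests can only contradict it, and no margin or interval rule fills the gap.

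The half-width of 0.38 SD and the non-significance rates in SD units depend only on 54 analysed patients per arm and a two-sided t test at 0.05. The figures in points depend on the assumed scale and SD, and the documents do not say whether 1 point would matter to patients. Whether 54 per arm is enough for a similarity claim cannot be settled from the documents: it would be for a margin of about 0.57 SD or wider, and not for a materially narrower one. In either case a non-significant difference test would not be the evidence.

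The consequence is limited to a secondary aim. It should be corrected, but the primary comparison and its sample size are untouched.

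**What to change.** In section 12.3, Aim 3, state that the between-arm difference in pain will be reported with its 95% CI, that the conclusion will rest on that interval, and that similarity will not be claimed from p>0.05. Name the pain scale there.

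Then choose one of two wordings for sections 4.1 and 12.1:

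- Reword the pain hypothesis as estimating the difference between the arms.
- Keep the word similar, but pre-specify and justify the largest difference regarded as unimportant, and require the CI to lie wholly within it. The table in step 5 shows what 54 per arm could deliver for a given margin.

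The cost is a few sentences, settled before results are seen, with no added patients or data. The downside is that the conclusion on pain may be less favourable: with a narrow margin the honest result may be that similarity was not shown.

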12.2 Sample Size Determination

Previous work suggests a failure rate of UGPIV of 40-44% and 5% for a small study of midlines placed in an ICU. We have therefore estimated a sample size based on a 25% difference in survival between midline catheter and UGPIV. **Based on a 25% difference in expected survival we will require 54 patients with a power of 0.8 and alpha of 0.05 assigned to each study arm (UGPIV and Midline).** Based on an expected 25% refusal rate and 30% of patients not being able to provide consent we will need to review and approach approximately 168 DVA patients. At BMC we place approximately 1600 ultrasound guided IVs per year making enrolling 54 in each arm highly feasible.

12.3 Statistical Methods

Statistical analysis and study measures

Catheter survival will be determined by how long an IV lasts prior to being removed measured in hours. We will include failures if a patient accidentally pulled out their access, thrombosis, infiltration or site bleeding, infection leading to removal, or there is too much pain reported resulting in removal. If it is known that a patient intentionally removes the IV or midline it will not be documented as a failure. We will report data based on a Kaplan Meir curve to

display catheter survival. We will use a t-test of means to compare failure rates between the two groups.

Direct Cost Analysis

A complete cost effectiveness analysis is beyond the scope of this proposal. We therefore wish to capture the direct costs and easily estimated costs associated with this change in practice.

We expect use of the midline catheter will be a cost effective change in practice.

Although more upfront costs, we expect that because the midline can dwell up to 29 days and is associated with fewer failures, it will be less expensive in the long run. We will obtain information from EPIC, as to whether a UGPIV or Midline fails. Nursing staff at BMC are required to file daily notes that include IV access type and location and daily events. We will have our study staff follow-up with patients or their medical teams to determine survival of the IV line if it cannot be determined from the medical record. If a failure occurs we will document the date and type of failure, i.e. thrombosis, infiltration, etc. We will then capture each additional IV that is placed and the associated billing from that procedure.

We additionally will capture the time spent placing each UGPIV in comparison to midline catheters. This will be accomplished by using the timestamp on the ultrasound at time of vessel identification, and then again at time of successful documentation of the catheter within the vessel. We will estimate for each failure of IV access a four-hour delay to have it replaced once hospitalized. Based on geographic cost, it is about \$100 per hour for inpatient hospitalization in Massachusetts. We additionally estimate the cost for staffing to be \$100 to replace a midline or UGPIV. We anticipate approximately a 5% failure in the midline group and 40% failure in the UGPIV group. We anticipate all midline failures will require repeat midline or CVC placement. We anticipate 10% of UGPIV will go on to get a CVC due to medical needs. We additionally estimate 33% of patients in the UGPIV group will require replacement during hospitalization. We anticipate one patient in the UGPIV to get a CVC and have a complication. CVC complications are reported to cost \$15,000 to \$50,000, however we will estimate a \$30,000 cost for each complication (example pneumothorax or line infection).¹²

Cost Estimate for 54 patients in UGPIV group:

54 initial UGPIV placements (54 x \$371): Projected outcomes: 5 patients progress to needing CVC (5 x \$1338), 17 subsequent failures getting repeat UGPIV (17 x \$371), 22 total failures at \$500 in estimated cost from delays in care and staffing (22 x \$500), 18 patients require additional access past 72-hour dwell time limit and get repeat UGPIV (18 x \$371). One CVC complication in the group of 54 patients: (1 x 30,000). = **Total Estimate: \$80,709**

Cost Estimate for 54 patients in Midline group:

54 initial midline placements (54 x \$1338), 3 failures with replacement cost and staffing and hospital delays (3 x \$1338 & 3 x 500), No complications expected or need for CVC. **Total Estimate: \$77,766**

We have projected a slight decrease in cost for midline placement at \$77,766 vs \$80,807 for 54 patients in this study. Based on these values with a power of 0.8 and alpha of 0.05 using a two

tailed t-test for independent means to predict a sample size with a SD of \$3,000 we will need to enroll 34 patients to adequately power our cost comparison group.

Aim 3: We will compare patient survey responses based on descriptive statistics, chi-square tests, or t tests as appropriate.

13 Ethics/Protection of Human Subjects

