6.1 Risks

Regardless if patients are placed in the ultrasound guided IV or Midline catheter group they will be at risk of complications of these devices. Each device carries the risk of failure (malposition), pain, bleeding, infection, or thrombosis (a blood clot forming). Serious complications are extremely rare and are not expected to occur in this study. The most likely serious complication, blood stream infection may occur in 0.5/1000 catheter days for midline and 0.2/1000 catheter days for ultrasound guided IVs. It is possible that either device may be placed improperly or malfunction during its intend lifetime. Although it is expected that some devices will fail during this study it is not considered a serious complication. If a device malfunctions, it is possible that medical solutions or blood may collect in the arm. Under very rare occurrences (limited to case reports) this can result in damage to the tissue around the catheter, the need of a surgery, or threaten the survival of the limb. In order to ensure the midline catheter does not enter into the axillary vein physicians will be trained to measure from the axilla to the target location. Each device is 10cm and there is a tape measure that will be used to ensure the procedure location is at least 10cm from the axillary vein. It is possible if measured incorrectly this could result in the midline catheter extending into the axillary vein. Despite the risks listed, both devices are routinely used as a part of medical care safely and it is extremely rare to have a serious adverse event from either device.

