It is mostly likely that if either device fails additional venous access may be required for medical care. If this occurs, it will be up to the medical team to determine which is the best option. One particular benefit of the midline catheter is that it may remain in use for up to 29 days while the ultrasound guided IV is used until there are signs and symptoms of phlebitis (warmth, tenderness, erythema, and or palpable cord), infiltration or a malfunctioning catheter. The site assessment guides the need for PIV replacement. The average ultrasound guided IV generally does not typically last longer than 3 to 4 days. Given the midline catheter may remain in place longer, it may be at slightly higher risk of having a clot form or developing an infection. If a clot or infection develops and is not identified and/or if left untreated it can be life threatening. In order to reduce these risks, we will follow our hospital guidelines for placement and monitoring of catheters. If any complication occurs, either the patient or their insurance will be responsible for any cost associated with a complication of the device.

Risks will be reduced by following hospital guidelines for the monitoring and care of venous access devices. There is also the risk of loss of confidentiality as covered in the consent form.

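### The primary failure list in section 12.3 omits malfunction, malposition and phlebitis, has no residual category, and conflicts with the Synopsis and section 6.1

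*Combined protocol and SAP*

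**What the plan says.** **Section 12.3 (Statistical Methods)** gives the events: "We will include failures if a patient accidentally pulled out their access, thrombosis, infiltration or site bleeding, infection leading to removal". The last item on its list is a catheter taken out because of pain. It names one non-failure: "If it is known that a patient intentionally removes the IV or midline it will not be documented as a failure". There is no category for other device-related causes.

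**Synopsis, Design/Methodology** measures catheter survival to "time to when a failed catheter is found to be dysfunctional", or to removal by hospital staff.

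**Section 6.1 (Risks)** says of both devices: "Each device carries the risk of failure (malposition), pain, bleeding, infection, or thrombosis", and adds: "It is possible that either device may be placed improperly or malfunction during its intend lifetime". It then says that a UGPIV stays in use until there are signs of phlebitis, "infiltration or a malfunctioning catheter".

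**Section 4.1.1** has the patient and nurse asked for the cause of failure. Its open-ended examples include patient preference and completed care. **Section 9** says research assistants do not judge failure themselves and rely on the clinical team. **Section 10.2** has any failure or complication entered in REDCap.

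**The concern.** The primary outcome is catheter survival, so the event definition decides what the trial measures. Three modes named in section 6.1 do not appear in 12.3, and the dysfunction that defines the event in the Synopsis is not there either.

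The clearest gap is a catheter that will not flush, with no thrombosis or infiltration identified. Section 4.1.1 notes that sites are flushed regularly to look for failures, so staff will meet such cases. In the Synopsis this catheter has reached its end point; under 12.3 it matches no listed cause. A UGPIV removed for redness or a palpable cord, without much pain, is in the same position.

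Someone must then decide whether the event is a failure or is censored. The two devices look different, and no blinded adjudication is described, so that decision could differ between arms.

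**Working it through.** **Step 1. Set the passages side by side.**

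| Mode | Synopsis | Section 6.1 | Section 12.3 list | Overlap with a listed cause |
|---|---|---|---|---|
| Malfunction or dysfunction | End of survival | Either device; end of use for the UGPIV | Absent | Partial: 6.1 says fluid or blood may collect in the arm, which could be coded as infiltration or bleeding. A blocked catheter with no identified cause is not covered |
| Malposition | Not named | Failure, each device | Absent | Partial: section 4.1 says infiltration can result from malposition, but not that it always does |
| Phlebitis | Not named | End of use, UGPIV only | Absent | Partial: tenderness is one of four signs and could lead to removal for pain; warmth, redness and a palpable cord need not |

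Some events in every row remain unclassified.

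**Step 2. Reproduce the planned sample size.** Section 12.2 gives a UGPIV failure rate of 40-44%, a 25% difference, power 0.8, alpha 0.05 and 54 per arm. I read the difference as absolute and the test as two-sided; neither is stated for the primary comparison. With p̄ the mean of the two rates:

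n = [1.96·√(2p̄(1−p̄)) + 0.8416·√(p1(1−p1)+p2(1−p2))]² / (p1−p2)²

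For 44% versus 19%, p̄ = 0.315, so n = (1.2875 + 0.5325)² / 0.0625, just above 53, which rounds up to **54**. The planned figure reproduces. For 42% versus 17% the formula gives 52, and for 40% versus 15% it gives 49.

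**Step 3. Illustrate an undercount.** The documents do not give the share u of failures that fall outside the list. I assume 10-30% and multiply the failure rates by (1−u):

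power = Φ{[(p1−p2) − 1.96·√(2p̄(1−p̄)/54)] / √([p1(1−p1)+p2(1−p2)]/54)}

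For u = 20% in both arms at 44% versus 19%, the counted rates are 35.2% and 15.2% and p̄ = 0.252. Power is Φ[(0.200 − 0.1638)/0.0813] = Φ(0.446) = 67.2%.

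| u, both arms | Counted rates (from 44% v 19%) | Difference, points | Power at 54 per arm | n per arm for 80% | Power at 54 per arm (from 40% v 5%) |
|---|---|---|---|---|---|
| 0 | 44.0% v 19.0% | 25.0 | 80.7% | 54 | 99.6% |
| 10% | 39.6% v 17.1% | 22.5 | 74.4% | 62 | 98.9% |
| 20% | 35.2% v 15.2% | 20.0 | 67.2% | 73 | 97.5% |
| 30% | 30.8% v 13.3% | 17.5 | 59.4% | 87 | 94.8% |

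The last column uses the 40% and 5% that 12.3 anticipates in its cost projection.

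**Step 4. Check the direction.** Take 44% versus 19% and u = 20% in one arm only.
- UGPIV arm only: 35.2% versus 19.0%, a difference of 16.2 points and power 47.3%.
- Midline arm only: 44.0% versus 15.2%, a difference of 28.8 points and apparent power 91.8%.

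The first dilutes the contrast and the second inflates it.

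**The case against.** The strongest reply is that 12.3 does not present its list as exhaustive. It says that certain events will be included, not that only those will be. The one event it rules out is known intentional removal by the patient. Its cost paragraph and section 4.1.1 both leave the causes open-ended, section 10.2 records any failure, and the Synopsis already covers dysfunction. The missing modes also overlap with listed ones.

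Much of this stands. A reader might infer that the list is closed and that true failures will certainly go uncounted. The text does not establish that; it leaves the classification unspecified. Section 6.1 also names phlebitis as an end of use for the UGPIV alone, and does not call it a failure of either device.

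Two further inferences are tempting but unsupported:
- **That the bias runs towards no difference because the UGPIV arm loses more events.** Section 6.1 assigns malposition and malfunction to both devices, no rates by arm are given, and step 4 shows that the sign can reverse.
- **That the link to the 40-44% failure rate is broken.** Section 12.2 does not say how the earlier work defined failure, so the list may or may not match it.

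The reply does not remove the gap. If the list is open, the primary event has no complete definition. Recording a cause in REDCap does not classify it, and the examples of failure in section 4.1.1 include reasons that are not device failures at all.

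**Conclusion.** The point holds as an incomplete and internally inconsistent definition of the primary event. Malfunction is the strongest part, because the Synopsis makes dysfunction the end point and 12.3 has no matching category. Phlebitis and malposition add a narrower residue after overlap with listed causes.

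Neither the direction nor the size of any bias can be derived from the documents. The loss of power from 81% to 74-59% assumes all-cause rates of 44% versus 19%, a two-sided two-proportion test and an undercount of 10-30%, equal in both arms; at 40% versus 5% power stays at about 95% or more. A reader could reach 29% power by placing a 30% undercount in the UGPIV arm alone at 44% versus 19%, but that combines unfavourable choices which the documents do not support. The 54 per arm does not itself depend on the list. The definition should be corrected because the correction is cheap and the item is the primary outcome.

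**What to change.** In 12.3, replace the list with one definition, reconciled with the Synopsis and sections 4.1.1 and 6.1:

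- **Failure for analysis:** loss of function, or removal, for any device-related reason. This includes non-flushing or other malfunction, malposition or dislodgement (including accidental pull-out), phlebitis, infiltration, bleeding, thrombosis, infection and pain.
- **Not a failure, censored at removal:** completion of care, patient preference, and intentional removal by the patient.

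Use the same codes in REDCap, so that each recorded cause maps to failure or censored in advance. This concerns classification for analysis only, not when a catheter should be removed.

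The cost is one sentence in 12.3 and matching codes. Counted failure rates will be somewhat higher.
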